# Synopsis

Title	Validation of a clinical prediction rule to identify patients with neck pain likely to benefit from cervical spinal manipulation: A randomized clinical trial
Study Duration	January 2025 – December 2026
Study location(s)	ActivePT – Rochester MN; ProActive PT – Syracuse NY; Active Therapy Alliance – Waco TX; Performance Physical Therapy – Las Vegas NV

Objectives	
 
Primary Objective: 
 
To determine the validity of a published clinical prediction rule (CPR) for identifying patients with neck pain who are likely to benefit from cervical thrust joint manipulation (TJM). Physical therapists commonly approach the management of patients with neck pain using manual therapy interventions directed at the cervical spine. These manual therapy techniques include joint mobilizations (non-thrust techniques) and TJM using a high-velocity, low amplitude therapeutic movement within or at end range of motion. The investigators hypothesize that patients who are positive on the rule and receive TJM will achieve greater improvement in 1-week and 4-week disability and pain than patients who are negative on the rule and receive TJM and compared to patients who are positive on the rule but receive an alternative exercise program without TJM.
 
 
 
Secondary Objectives         
 
To compare the long-term (6-month follow-up) clinical outcomes and healthcare utilization based on status on the CPR and the treatment received. The investigators hypothesize that patients who are positive on the CPR and receive TJM will demonstrate improved disability and lower health care utilization than patients who are negative on the CPR and receive TJM will demonstrate improved to patients who are positive on the CPR and receive TJM will achieve greater improvement in 6-month pain levels and receive TJM and compared to patients who are positive on the CPR and receive TJM will achieve greater improvement in 6-month pain levels and a reduction in fear-avoidance beliefs compared to patients who are negative on the CPR and receive TJM will achieve greater improvement in 6-month pain levels and a reduction in fear-avoidance beliefs compared to patients who are negative on the CPR but receive an alternative exercise rogram without TJM.
 

Number of Subjects	exercise program without TJM.
	-

	Inclusion criteria:
	1. Ages 18 to 70
	2. Primary complaint of neck pain with or without unilateral
	upper extremity symptoms
	3. Neck Disability Index (NDI) score $\geq$ 10 out of 50 points
	
 
Numeric Pain Rating Scale ≥ 2 out of 10
 

	Exclusion criteria:
	1. History of whiplash injury within the past 6 weeks
	2. Diagnosis of cervical spine stenosis
	3. Bilateral upper extremity symptoms
	4. Red flags noted in the patient's Neck Medical Screening
	Questionnaire (i.e. tumor, fracture, rheumatoid arthritis,
	osteoporosis, severe atherosclerosis, dizziness, diplopia,
	drop attacks, bilateral numbness, nausea, prolonged
	history of steroid use)
	5. Evidence of central nervous system involvement, to include
	hyperreflexia, sensory disturbances in the hand, intrinsic
	muscle wasting of the hands, unsteadiness during walking,
	nystagmus, loss of visual acuity, impaired sensation of the
	face, altered taste, the presence of pathological reflexes
Main Inclusion/Exclusion	(i.e. positive Hoffman's and/or Babinski reflexes)
Criteria	6. Two or more positive neurological signs consistent with
	significant nerve root compression, including any two of
	the following:
	a. Muscle weakness involving a major muscle group of
	the upper extremity
	a. Diminished upper extremity muscle stretch reflex
	(biceps brachii, brachioradialis, or triceps reflex)
	a. Diminished or absent sensation to pinprick or light
	touch in any upper extremity dermatome
	7. Prior neck surgery
	8. Current pregnancy, recent pregnancy (within the last 6
	months), or currently lactating
	9. Pending legal action pertaining to their neck pain
	10. Inability to read English at an 8th grade reading level (any
	participant unable to read the informed consent form
	which will be written at an 8th grade level)
	11. Inability to legally provide informed consent for any other
	reason
	12. Inability to comply with the treatment and follow-up
	schedule
	1

# 1.0 BACKGROUND AND RATIONALE

Neck pain is a prevalent and often debilitating condition affecting a substantial portion of the adult population worldwide, with estimates indicating a global prevalence ranging from 203 to 223 million people. This prevalence is projected to increase globally to 32.5% by 2050. With an age-standardized annual incidence of 906.4 (812.5 to 1012.5) per 100,000 population, the United States ranks amongst the highest worldwide. Most individuals with disabling subacute or chronic neck pain experience reduced pain intensity over a year, but one-quarter have unfavorable outcomes.

The economic burden of neck pain is significant, contributing to prolonged disability, lost work time, and increased healthcare costs. In 2016, musculoskeletal conditions accounted for \$380.9 billion in healthcare spending in the U.S., with neck and back pain contributing to a substantive burden of \$134.5 billion.

The *Guide to Physical Therapist Practice* indicates that interventions such as mobilization/manipulation, therapeutic exercise, neuromuscular re-education, traction, and a variety of modalities are utilized by physical therapists to manage patients with neck pain. Although these interventions are largely accepted as the standard of care for patients with neck pain, high quality evidence from randomized controlled trials (RCTs) that investigate these interventions are frequently inconclusive. Furthermore, guidance in selecting the most beneficial interventions for an individual patient is also lacking, potentially resulting in less effective intervention strategies for these patients. Clinical practice guidelines recommend manual therapy for managing neck pain, including cervical thrust joint manipulation (TJM). However, limited information on when and for whom cervical TJM is most beneficial leads to inconsistent clinical practice. The development of a clinical prediction rule (CPR) by Puentedura et al. (2012) identified patients with neck pain likely to benefit from cervical TJM based on four criteria: symptom duration less than 38 days, positive expectation that TJM will benefit them, side-to-side difference in cervical rotation range of motion of 10° or greater, pain with posteroanterior spring testing of the middle cervical spine.  If 3 of the 4 variables were present (+LR 13.5) the chance of experiencing a successful outcome improved from 39% to 90%. However, this CPR has not yet been validated, which presents a critical barrier to its widespread adoption in clinical practice.

Although the initial findings based on the development of a cervical spine TJM CPR may be exciting, McGinn et al have suggested there is a three-step process for developing and testing a CPR prior to promotion for wide-spread implementation of the rule in clinical practice. The first step is to create the CPR. The second step is to validate the CPR in a different population of patients and the third is assessing the impact of the rule on clinical behavior. At this point, investigators need to validate the CPR within a varied and generalizable population of patients. This step is important to ensure the results found in the initial study can be validated in another sample with replicable findings.

The purpose of this validation RCT in which patients will be randomly assigned to receive cervical spine TJM followed by exercise or low-grade non-thrust mobilizations (NTM) followed

by exercise will be to investigate the validity of the previously developed CPR. Patients will also be classified as to their status regarding the CPR. If the CPR is indeed meaningful, patients who are positive on the CPR and receive cervical spine TJM should experience improved outcomes compared to patients who are negative on the CPR and receive cervical spine TJM, and compared to patients who are positive on the CPR but receive the NTM intervention believed to be effective for another subgroup of patients with neck pain. If its use results in similar dramatic improvement across patient populations, investigators will now have an effective tool to enhance clinicians' prognostic assessment and an effective treatment strategy.

If the proposed aims are achieved, the impact on the field of physical therapy and the management of neck pain will be substantial. The validation of the CPR will refine our understanding of the predictors of successful outcomes for cervical TJM in patients with neck pain, potentially contributing to decreased chronicity, reduced healthcare costs, and improved standardization of clinical practice.

Effective implementation of the CPR could lead to reduced healthcare costs by minimizing unnecessary treatments and focusing resources on interventions most likely to yield positive outcomes. Patients identified as likely responders to cervical TJM are expected to show significant improvements in disability and pain, thereby decreasing long-term healthcare utilization. A recent meta-analysis comparing exercise therapy with manual therapy, including manipulation (TJM) and mobilization NTM), for neck pain found manual therapy and exercise to be cost-effective options. Early and accurate identification of patients who will benefit from cervical TJM may prevent the progression of acute neck pain to chronic conditions, reducing the overall burden of neck pain on individuals and healthcare systems.

Validating this CPR for cervical TJM could significantly enhance clinical decision-making, ensuring that cervical TJM is used effectively. This addresses a crucial gap in the literature and has the potential to improve both scientific understanding and clinical practice. By providing a reliable tool to identify patients with neck pain most likely to benefit from cervical TJM, clinicians can make more informed decisions, leading to more effective and efficient treatments. The results of this study will inform updates to clinical practice guidelines, ensuring they reflect the most current and validated evidence, which can lead to standardized care practices across different clinical settings and improve the quality of care for patients with neck pain.

Investigators will conduct a multi-center randomized clinical trial (RCT) to assess the effectiveness of a previously developed clinical prediction rule (CPR) for identifying patients with neck pain likely to respond to cervical spine TJM. The investigators will compare clinical outcomes within a randomized block design between two comparison groups: 1) cervical joint manipulation + exercise (MTE) and 2) cervical joint non-thrust mobilizations + exercise (MoE). This research will serve to validate the effectiveness of cervical TJM across different patient populations using rigorous design and research controls. The overall purpose of this trial will be to determine if patients who are identified as those likely to improve with cervical TJM (i.e. positive on the CPR) respond better to TJM or an alternative form of NTM treatment commonly used in physical therapy with demonstrated effectiveness. This information will have

immediate utility for clinicians to select the optimal treatment for individuals with neck pain and identify early those most likely to be successfully treated.

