# 2.0 STUDY OBJECTIVES

**Primary Objective:** To determine the validity of a CPR for identifying patients with neck pain who are likely to benefit from cervical TJM. The investigators hypothesize that patients who are positive on the rule and receive TJM will achieve greater improvement in 1-week and 4-week disability and pain than patients who are negative on the rule and receive TJM plus exercise *and* compared to patients who are positive on the rule but receive an alternative NTM plus exercise program without TJM.

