# Identification of the Status on the Rule

As in the initial study, patients meeting at least three of the following criteria will be classified as meeting the CPR (+) for cervical TJM. Patients meeting two or fewer criteria will be classified as not meeting the CPR (-):

1. Symptom duration less than 38 days

- 2. Positive expectation that TJM will help
- 3. Side-to-side difference in cervical rotation range of motion of 10° or greater
- 4. Pain with posteroanterior spring testing of the middle cervical spine

Based on previous results, these criteria increase the likelihood of a *successful* response with cervical TJM from an initial 39% to 90%. Patients who rated their perceived recovery on the GROC as "a very great deal better", "a great deal better", or "quite a bit better" (i.e., a score of +5 or greater) were judged as a success. This degree of improvement over a 2–4-day period was deemed to provide an adequate distinction between patients responding to the intervention and those simply benefiting from the favorable natural history of neck pain. For those *not* meeting *at least 3* of the 4 criteria, the likelihood of a successful response only rose from 39% to 43% (1 criterion) or 68% (2 criteria). Once the examination is complete patients will be randomly assigned to one of the two groups regardless of their status on the CPR: 1) MTE or 2) MoE.

A random number generator will be used to conduct the randomization, and this procedure will be conducted prior to the initiation of the study. The randomization will be concealed according to the following procedure:

- The group assignment will be recorded on a label that is affixed to a 3.5 X 5-inch index card which will be folded in half. The folded index card will then be placed inside the envelope, and the envelope will be sealed.
- Once the baseline examination is complete, the randomization envelope will be handed to a treating therapist who is blinded to the initial baseline examination; she/he will open the envelope, and the treatment will begin according to group assignment under the supervision of the treating therapist.

Treatment will be initiated immediately following the baseline examination, unless prohibited by time constraints; in this case the patient will be scheduled for a follow-up session within 24 to 48 hours of the initial examination to receive the first treatment.

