Specific Aims: Primary Aim #1: To determine the validity of the clinical prediction rule for identifying patients with neck pain who are likely to benefit from C-TJM. Pain and Disability. The investigators will examine the primary aim with separate random intercept linear mixed models with treatment group (MTE vs. MoE), status on the CPR (positive or negative) and time (baseline, 1-week and 4weeks) as fixed effects. The dependent variables will be pain (NPRS) and disability (NDI score). The hypothesis of interest is the group \* CPR status \* time interaction. The primary dependent variables are the 1-week NPRS and NDI scores to mirror the follow-up used in Cleland and colleagues' study. The investigators will assess the NPRS and NDI scores after 4 weeks to determine whether a patient's status on the rule predicts outcome at a longer follow-up. The investigators will perform planned pairwise comparisons at each follow-up period by using the Bonferroni test of inequality. The investigators hypothesize that patients who are positive on the rule and receive TJM will achieve greater improvement in immediate (1-week) and 4-week pain and disability, than patients who are negative on the rule and receive TJM, and compared to patients who are positive on the rule but receive an alternative exercise program without TJM. Because the rule is believed to be specific to a TJM intervention, investigators hypothesize that outcomes among those receiving the MoE treatment would not differ on the basis of a patient's status on the rule.

Secondary Aim #1: To compare the long-term (6-month) pain and disability scores (clinical

outcomes) and healthcare utilization based on status on the clinical prediction rule and the treatment received. The investigators will examine this with random intercept linear mixed models with treatment group (MTE vs. MoE), status on the CPR (positive or negative), and time (baseline and 6-months) as fixed effects. The dependent variables will be pain (NPRS) and disability (NDI) scores. The investigators will perform planned pairwise comparisons at each follow-up period by using the Bonferroni test of inequality. The hypothesis of interest is the group \* status on CPR \* time interaction. The investigators hypothesize that patients who are positive on the rule and received TJM would experience greater improvement at 6-months than patients who are negative on the rule and received the MoE program without TJM.

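### The two contrasts that state what a meaningful rule should show can both hold with no effect modification, and nothing makes the named interaction decisive

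*Combined protocol and SAP*

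**What the plan says.** Section 1.0 (Background and Rationale) states what should follow from a useful rule: "If the CPR is indeed meaningful, patients who are positive on the CPR and receive cervical spine TJM should experience improved outcomes compared" with two comparators, CPR-negative patients given TJM and CPR-positive patients given NTM. Section 2.0 turns the same pair into the primary hypothesis. Its first half is that CPR-positive patients in the manipulation arm "will achieve greater improvement in 1-week and 4-week disability and pain than patients who are negative on the rule and receive TJM plus exercise". The other comparator is the CPR-positive patients given NTM plus exercise.

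Section 7.0, Primary Aim #1, repeats the pair and adds two things. It says "The hypothesis of interest is the group \* CPR status \* time interaction". It also makes a prediction for the comparison arm: "Because the rule is believed to be specific to a TJM intervention, investigators hypothesize that outcomes among those receiving the MoE treatment would not differ" by rule status. On follow-up tests it says "The investigators will perform planned pairwise comparisons at each follow-up period by using the Bonferroni test of inequality", without giving the number of comparisons.

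Under Sample Size and Power, the trial is sized on a difference between any two of the four cells: 10 NDI points, SD 12, two-sided alpha 0.05, 90% power, 31 per cell, with 140 recruited (35 per cell).

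Symptom duration under 38 days is one of the four criteria of the rule, of which three are needed. The section on identifying rule status recognises that some patients may improve as "those simply benefiting from the favorable natural history of neck pain".

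**The concern.** A rule that selects treatment must show that the TJM-versus-NTM effect differs by rule status. Neither stated contrast measures that alone. CPR-positive versus CPR-negative within TJM is not randomised, and it includes any difference in natural course between recent-onset and longer-standing pain. TJM versus NTM within CPR-positive patients is randomised, but it includes any benefit of TJM that all patients share. A prognostic marker combined with a general TJM benefit therefore yields both results.

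The trial is meant to tell clinicians whom to manipulate and to inform guidelines. If two significant pairwise results stand beside a non-significant interaction, the plan does not say which governs. A marker of faster recovery could then be reported as a validated treatment-selection rule.

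**Working it through.** **Inputs.** SD of NDI change 12, difference 10, alpha 0.05 two-sided, 90% power, 31 per cell required (Sample Size and Power); 35 per cell recruited (section 4.0); NDI minimum important difference 5.5 to 7 points (section 4.0, outcome measures). The documents give no size for natural-course or general TJM effects, so 3, 5.5, 7 and 10 points are assumptions, read on the same NDI scale as the SD.

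**The plan's own figure.** n = 2 × (1.960 + 1.282)² × 12² / 10² = 30.26, so 31 per cell. It reproduces, as the size for a pairwise difference.

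**Algebra.** Let P be the extra improvement of CPR-positive patients in either arm, T the extra improvement from TJM in either stratum, and I the interaction. Mean improvement relative to CPR-negative/MoE:

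| | MTE (TJM) | MoE (NTM) |
|---|---|---|
| CPR-positive | P + T + I | P |
| CPR-negative | T | 0 |

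- CPR+/TJM minus CPR−/TJM = P + I
- CPR+/TJM minus CPR+/NTM = T + I
- CPR+ minus CPR− within MoE = P
- MTE minus MoE within CPR− = T
- (MTE − MoE in CPR+) minus (MTE − MoE in CPR−) = I

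With I = 0 the two stated contrasts reduce to P and T, and both are positive whenever P > 0 and T > 0. Only the last line isolates I.

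**How often this happens.** Four cell means were simulated on 1-week change with I = 0, P = T, SD 12, 35 per cell and pooled t tests on 136 degrees of freedom. The standard error is 12 × √(2/35) = 2.87 for a pairwise contrast and 2 × 12/√35 = 4.06 for the interaction. The plan does not state the number of comparisons, so results are shown unadjusted / Bonferroni over six pairs. The MoE check uses the same threshold as the two contrasts.

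| P = T (points) | Both contrasts significant | Also MoE difference not significant | Also interaction significant in the hypothesised direction |
|---|---|---|---|
| 3 | 7.5% / 1.4% | 7% / 1.4% | 1.7% / 0.7% |
| 5.5 | 31% / 11% | 20% / 10% | 2.4% / 2.0% |
| 7 | 53% / 25% | 20% / 18% | 2.5% / 2.4% |
| 10 | 89% / 67% | 6% / 16% | 2.5% / 2.5% |

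In the last column the interaction is tested at two-sided 0.05 throughout, and the third column's MoE check is not imposed.

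**Power of the decisive contrast.** Its variance is 4 × 12²/n, twice that of a pairwise difference. At 35 per cell, power is about 69% for I = 10 and 40% for I = 7; at 31 per cell, about 63% and 36%. With P = T = 0 and I = 10 at 35 per cell, both pairwise contrasts are significant in 88% of trials unadjusted, and in about 24% of those the interaction is not. Two positive pairwise results beside a null interaction can thus occur under a true interaction as well as under none.

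**The case against.** The strongest reply is that Primary Aim #1 already contains the right test. It names the three-way interaction as the hypothesis of interest and lists the pairwise comparisons after it. It also predicts no CPR difference within MoE, which faster natural recovery in both arms would contradict. Section 1.0, read strictly, states a consequence of validity and not a sufficient condition. All of this stands, and it rules out several stronger readings that a reader might infer:

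- *That the plan ignores effect modification.* It does not; the interaction is named.
- *That the plan would validate a worthless rule in up to 89% of trials.* That figure counts the two contrasts alone and assumes that NTM is worse by the full 10-point design difference even in CPR-negative patients. Under the full predicted pattern the rate at 10 points is 6%/16%. With unequal effects it can be small: at P = 7 and T = 3, both contrasts are significant in 16%/4%; at P = 7 and T = 0, in 2.4%/0.4%.
- *That only TJM versus NTM in CPR-negative patients could expose the problem.* The predicted comparison within MoE can expose it too.
- *That the early check against natural history was dropped.* The global rating of change is still collected in both arms before session 2, at 2–4 days, although no analysis at that time is specified.

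What the reply does not supply is a decision rule. No section says that a non-significant interaction, or a CPR difference within MoE, defeats the claim. The MoE prediction is a weak guard, because non-significance with 35 against 35 is poor evidence of no difference: at P = 7 an unadjusted test misses the difference in about 32% of trials.

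**Conclusion.** The point holds as a missing decision rule, not as a missing test. The rationale and objectives state validity through two contrasts that equal P + I and T + I, and the sample size is built on a pairwise difference. With zero interaction and equal effects of 3 to 10 points, the two contrasts are met in 7.5% to 89% of trials unadjusted and 1.4% to 67% with Bonferroni over six. Adding the MoE prediction leaves 6% to 20% and 1.4% to 18%. Making the interaction a condition leaves at most about 2.5%.

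These rates rest on assumed values of P and T. Recent onset is only one of four criteria, so a prognostic gain is plausible but its size is unknown. The simulation covers one outcome at one time, not the full mixed model or the 4-week and pain hypotheses.

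**What to change.** In sections 1.0 and 2.0 and in Primary Aim #1, state that validity for selecting TJM is judged on the 1-week contrast (MTE − MoE in CPR-positive) minus (MTE − MoE in CPR-negative). It should be reported with its estimate and confidence interval, and be significant in the hypothesised direction. Treat the pairwise contrasts as supportive, report MTE versus MoE in CPR-negative patients alongside them, and label CPR+/TJM versus CPR−/TJM as a non-randomised prognostic comparison.

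This is a change of wording; it needs no new data or model. The cost, which the plan should state, is that a positive claim becomes harder to reach: power is about 69% for 10 points and 40% for 7 at 35 per cell (63% and 36% at 31), not the 90% given for a pairwise difference. Restoring 90% for a 10-point interaction would take 2 × 30.26 = 60.5, so 61 per cell or 244 patients before dropout. If that is out of reach, the lower power should be disclosed and a non-significant interaction reported as inconclusive, with its interval.
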